- **Study Design:** A randomized, double-blind, placebo-controlled, parallel-group study of flexible dose mixed salts amphetamine (5-60 mg) adjunctive to antidepressant therapy among adult outpatients with major depressive disorder responding inadequately to current antidepressant therapy.

Fig. 1: Treatment Groups

Visit	Phase	Weeks	Group	Group	Procedures
		on med	1	2	
V1		Scr			Inclusion/Exclusion
V2		0			Baseline measurement + disp.
V3	Ι	1	MSA	PBO	Measure effect of 1 week on study med + disp.
V4	Ι	2	MSA	PBO	Measure effect of 2 weeks on study med + disp.
V5	Ι	3	MSA	PBO	Measure effect of 3 weeks on study med + disp.
V6	II	4	MSA	MSA	Measure effect of 3 weeks on study med + disp.
V7	II	5	MSA	MSA	Measure effect of 3 weeks on study med + disp.
V8	II	6	MSA	MSA	Measure effect of 3 weeks on study med
V9		(8)			Safety follow-up

Fig. 2: Study Design Overview

The treatment phase of the study consists of 2 phases (21 treatment days per phase). Study Phase 1 will consist of visits 2 (baseline) through 5. Study Phase 2 will consist of visits 6 through 8. There will be a follow-up visit 2 weeks following visit 8. There is a one-week interval between study visits, with a scheduling window of \pm 3 days allowed.

Mixed salts amphetamine is FDA-approved for Attention Deficit-Hyperactivity Disorder (ADHD) and superior in efficacy to placebo; therefore, comorbid ADHD will be statistically controlled as a continuously-variable covariate, but will not be considered an exclusionary condition.

The primary analysis will be a repeated measures analysis of variance using a mixed-effects model (PROC MIXED-MMRM). The primary outcome measure will be the MGH-CPFQ total score at baseline and the MGH-CPFQ total score at the end of the trial. The independent variables will be the study visit, the treatment in the previous phase, and treatment assignment. The variance covariance matrix for the repeated measures will be unspecified.

Enrollment Period: The enrollment period is estimated to be 6 months. The last patient is expected to complete the study by March 31, 2010.

Number of Subjects: 40 subjects will be randomized (20 to each treatment arm). Additional subjects may be consented to allow for screen failures. Subjects who terminate early post-randomization will be replaced only sufficiently to ensure a total number of 24 (12 to each treatment arm) evaluable subjects.

Duration of Subjects' Study Participation: There will be a total of 9 study visits over a period of 9 weeks.

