- 11) Pregnant or breastfeeding women.

Study Procedures: Figure 3 shows study procedures to be performed at each visit. No study procedures will be performed until a subject signs the informed consent document.

Screen visit (Visit 1): Medical and psychiatric history will be taken, a physical examination and vital signs will be performed and lab tests done. Lab tests include CBC, CMP, urine drug screen and urine pregnancy test for females of childbearing potential. If a subject has had the required lab tests performed within the past 3 months and can produce the results, lab procedures may be waived at the screening visit for that patient (except urine pregnancy test). The HDRS-17 score upon screening will be used to determine entry eligibility (see inclusion criteria). Beyond the patient's verbal report, we will attempt to obtain medical records (e.g., previous clinician or pharmacy records) to document adequate dose and duration of previous/current ADT.

Study Phase 1

Baseline visit (Visit 2): Screened and eligible subjects will return one week after the screening visit. At this visit (provided entry criteria continue to be met) subjects will be randomized in double-blind fashion to one of two treatment groups:

- Group 1: MSA during both phases; or
- Group 2: PBO during Phase 1 followed by MSA during phase 2

Study drug will be dispensed to the subject in sufficient quantity to last until the next study visit (7 days +/-3).

Study visits 3-5: Following the baseline visit, subjects will return at one-week intervals for study visits 3-5. Study procedures to be performed are reflected in Figure 3. Phase 2 study drug is dispensed at study visit 5.

Study visits 6-8: Subjects will return at one-week intervals for study visits 6-8. Study procedures to be performed are reflected in Figure 3. At visit 8, all subjects will receive instructions for tapering the dose of the MSA to avoid potential difficulties from abrupt discontinuation of the study drug.

Study visit 9: Subjects will return two weeks following visit 8 for a safety follow-up check. Procedures to be performed are reflected in Figure 3.

If a subject withdraws or is terminated early from the study, visit 9 procedures will be performed at the final study visit.

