All concomitant medications taken during the study will be recorded in the case report form, along with dosage information and start and stop dates. Subjects requiring excluded drugs will be discontinued from the study. Medication management and clinical ratings will be performed by the study clinicians.

Subjects who complete the trial will be offered referrals to qualified physicians for the purposes of continued care. At the conclusion of Visit 8, study blind will be removed by an unblinded study staff member for facilitation of ongoing treatment by patient's selected follow-up care provider. At Visit 8, study subjects will be provided a one-month prescription for the dose of MSA they are currently prescribed in the study to ease transition to their follow-up care physician.

At the end of the study, subjects will be followed for up to three months while an appointment can be secured with their original treatment provider or with one referred by the research center.

Investigational Product(s), Dose and Mode of Administration, Duration of Treatment with Investigational Product(s): Based upon clinical judgment and ascertained between clinician and patient, study drug will be dosed as follows: The total daily dosage of study drug will be 5-60 mg, supplied in 5 and 10 mg tablets of MSA or matching PBO.

Total daily dosing of the concurrent ADT will be as follows: escitalopram 10-40 mg; fluoxetine 20-80 mg; paroxetine CR 25-100 mg (paroxetine 20-80 mg may be substituted if paroxetine CR is not available); sertraline 100-400 mg; venlafaxine XR 150-600 mg; desvenlafaxine 50-200mg; citalopram 20-80 mg; or duloxetine 60-180 mg; bupropion 150-450 mg; mirtazapine 15-45 mg, tricyclics (standard dosing, individually per label instructions).

The dose of MSA begins at 5mg BID. MSA dose range will be 5mg-20mg BID or TID, not to exceed 60mg per day in addition to the stable dose of ongoing ADT. Each study medication tablet will be 5 or 10 mg of MSA or PBO. Upward titration will be based upon physician's clinical judgment and confirmed by patient's consent.

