Subjects unable to tolerate the study medications will be withdrawn from the study. Every effort will be made to encourage patients to comply with this dosage regimen and to take all study medications and their ongoing concomitant ADT as instructed. All patients will be instructed to return any excess medication at each visit. A pill count will be done to corroborate the study drug record. Protocol violation will be defined as less than 80% compliance by pill count.

MSA doses will be custom-tapered per physician's discretion starting at visit 8.

The study medication packager will use a block randomization scheme to distribute the kits within each box/block.

Risk/Safety Information: The principal investigator and subinvestigators are responsible for monitoring the safety of the subjects who have entered this study and for alerting the IRB of any event that meets IRB reporting criteria. The investigator is also responsible to follow, through an appropriate health care option, adverse events that are serious or that caused the subject to discontinue before completing the study. The subject should be followed until the event resolves or is explained. Frequency of follow-up is left to the discretion of the investigator.

Monitoring and Reporting of Adverse Events and Serious Adverse Events:

Adverse Events:

All observed or volunteered adverse events, regardless of suspected causal relationship to study drug, will be recorded on the case report form and reported to the IRB if reporting criteria are met.

Serious and/or Unexpected Adverse Events:

Study site personnel will report to the IRB any serious and/or unexpected adverse event following IRB reporting guidelines. A serious adverse event is any adverse experience that results in one of the following outcomes, or is significant for any other reason:

- Death
- Initial or prolonged inpatient hospitalization
- A life-threatening experience (that is, immediate risk of dying)
- Severe or permanent disability
- Cancer
- Congenital anomaly

Serious adverse events occurring after a subject is discontinued from the study will not be reported unless the investigator feels that the event may have been caused by the study drug or a protocol procedure.

Unblinding Procedure

Unblinding may be performed only by unblinded site personnel, under two conditions:

- If necessary for treatment of the subject in the event of a medical emergency

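### Visit 8 gives conflicting MSA instructions: a taper for all subjects, and a one-month prescription at the current dose

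*Combined protocol and SAP*

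**What the plan says.** Three statements in the combined protocol and SAP govern MSA at Visit 8.

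- Study Procedures, Study visits 6-8: "At visit 8, all subjects will receive instructions for tapering the dose of the MSA to avoid potential difficulties from abrupt discontinuation".
- Study Procedures, on subjects who complete the trial: "At Visit 8, study subjects will be provided a one-month prescription for the dose of MSA they are currently prescribed in the study". The stated purpose is to bridge to a follow-up physician, and the blind is broken at the same visit to support continuing care.
- Investigational Product(s), Dose and Mode of Administration: MSA will be tapered on a schedule left to the physician's "discretion starting at visit 8".

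The dose range is stated as: "MSA dose range will be 5mg-20mg BID or TID, not to exceed 60mg per day". After the study, "subjects will be followed for up to three months while an appointment can be secured".

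On supply at Visit 8, Fig. 1 notes dispensing at Visits 2 to 7 and none at Visit 8, while Fig. 3 marks study drug as dispensed at Visits 2 to 8.

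On timing, Study Design states: "There will be a follow-up visit 2 weeks following visit 8". Fig. 3 marks EKG at Visits 1 and 9 only. The row for laboratory tests and urine drug screen is also marked only at those two visits. Vital signs and weight, C-SSRS and adverse events are marked at Visit 9 and at earlier visits. Subjects who leave early have the Visit 9 procedures at their last visit.

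**The concern.** One rule lowers the dose from Visit 8 and the other holds it for a month. The protocol does not assign subjects to either.

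The main stake is patient safety. A completer can be told to come off a stimulant and be handed a full-dose month of it at the same visit. The Background itself describes stimulant misuse as a common worry among prescribers. A completer who continues instead has no stated plan for the end of the month, although finding a prescriber may take up to three months.

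The secondary stake is how Visit 9 safety data can be read. EKG change is a listed safety outcome, and for completers the Visit 9 EKG and laboratory values are the only scheduled ones after screening. Without a rule, a reader cannot tell from the protocol whether those values were meant to be taken on MSA or after it had been withdrawn.

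**Working it through.** The plan gives no figure to reproduce. The check is a comparison of the text plus simple arithmetic.

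**1. Can both rules be met for one subject?**

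| Feature | Taper rule | Prescription rule |
|---|---|---|
| Who | all subjects | study subjects, with no subgroup named |
| When | from Visit 8 | at Visit 8 |
| Dose after Visit 8 | falling, schedule discretionary | unchanged for one month |
| Purpose | avoid stopping suddenly | carry over to a follow-up physician |

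Four ways of reconciling them were tried.

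- *Taper instructions are for later use.* The dosing section starts the taper at Visit 8.
- *Only those who stop will taper.* Study visits 6-8 addresses all subjects.
- *The prescription is the taper supply.* It is written for the current dose and for a different purpose.
- *Discretion settles it.* The discretion covers how the dose is tapered; that it will be tapered is stated as a fact.

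None fits all three statements.

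**2. Which supply is intended?** Fig. 1 has no dispensing at Visit 8 and Fig. 3 has it. A subject may therefore leave with a prescription alone, or with study tablets and a prescription.

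**3. Size of a surplus.** Let D be the daily dose at Visit 8. A 30-day month (assumption) supplies 30 × D.

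- At the cap: 30 × 60 = 1,800 mg.
- At the starting dose of 5 mg twice daily: 30 × 10 = 300 mg.

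If the taper uses study tablets dispensed at Visit 8, the whole amount is surplus. If it draws on the prescription, the surplus is that amount less what the taper consumes.

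**4. Does Visit 9 fall within the month?** Days are from Fig. 3.

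- Interval: 56 − 42 = 14 days.
- Supply left from a 30-day month at full dose: 30 − 14 = 16 days.
- If a month is 28 to 31 days and the ±3 day window also applies to Visit 9 (assumptions): 28 − 17 = 11 to 31 − 11 = 20 days left.

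Visit 9 falls within the month in every case.

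**5. Intended dose at Visit 9.** Under the prescription rule it is D. Under the taper rule it lies between 0 and D, and reaches 0 only if the taper ends within the interval, which the protocol does not say. The range for one subject is therefore 0 to D. Across subjects D can be as high as 20 mg × 3 = 60 mg/day.

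**6. Which data are touched?** Those marked at Visit 9: EKG, laboratory tests, urine drug screen, vital signs and weight, C-SSRS and adverse events. The MGH-CPFQ and the other efficacy scales end at Visit 8, so they precede any difference between the rules.

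**The case against.** The strongest reply is that giving a supply and taper instructions at one visit is not contradictory in itself. The instructions could be a fallback in case follow-up care falls through. That is a sensible clinical reading, and a site might well adopt it. The protocol does not state it, however, and the Visit 8 start date in the dosing section goes against it.

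A reader might infer more than the documents support in four ways.

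- *The conflict is what leaves the Visit 9 dose open.* Flexible dosing and a taper of unstated length would leave it open under the taper rule alone. Much of the 0-60 mg/day span is variation between subjects; what the conflict leaves undefined is whether a given subject is meant to be on or off MSA.
- *The conflict costs the trial its EKG comparison with placebo.* Both groups take MSA in Phase 2, so Visit 9 cannot provide that comparison under either rule. This is a separate limitation of the schedule.
- *Exposure at Visit 9 will be unknown.* Visit 9 is inside the study ("There will be a total of 9 study visits over a period of 9 weeks"), Fig. 3 marks concomitant therapy and drug accountability there, and "All concomitant medications taken during the study will be recorded in the case report form, along with dosage information and start and stop dates". Actual intake should largely be recoverable.
- *Subjects are stopped abruptly at Visit 8.* Neither rule does that. The gap is what happens when the month runs out.

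It would equally be too narrow to confine the data effect to the EKG, since the other Visit 9 safety measures share it. The point also does not extend to early terminators, whose EKG is taken at their final visit and may fall during treatment, including on Phase 1 placebo.

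**Conclusion.** The point holds: the Visit 8 rule is wrong as written, and the severity is minor. For each subject who reaches Visit 8, two instructions apply that cannot both be followed, and the dispensing entries disagree as well. The number affected is not stated: 40 are to be randomized, and replacement is meant to secure 24 evaluable, but neither figure is a count of subjects reaching Visit 8.

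Patient safety is the main consequence, with surplus stimulant of up to 1,800 mg per tapering subject (60 mg/day, 30-day month, none of it used for the taper). The effect on data is secondary: Visit 9 safety measures lack a defined on- or off-MSA status. The documents do not support extending the point to the primary endpoint, other efficacy results or safety data from Visits 3 to 8.

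**What to change.** Amend Study Procedures and the dosing section so that one rule applies to each subject.

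- Subjects continuing with a follow-up prescriber receive the bridging prescription and do not taper at Visit 8. State a taper plan for those whose month ends before a prescriber is secured.
- All others taper from Visit 8 with a defined taper supply and receive no full-dose prescription.
- Make the Visit 8 dispensing entries in Fig. 1 and Fig. 3 agree with this rule.
- Record MSA dose and date of last dose at Visit 9.
- Report Visit 9 safety data descriptively by on/off MSA, and do not present them as a comparison of MSA with placebo.

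Doses at Visit 9 will still differ between subjects; the gain is that each subject's status is defined and recorded. The cost is a few sentences, one corrected table entry and one or two case report form fields. No visit or procedure is added.

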Study Assessments and Primary Endpoints: The difference in absolute change in score from baseline to endpoint in the MGH-CPFQ between the MSA and the PBO groups is the primary endpoint. Key secondary endpoints will be difference in absolute change from baseline in MADRS score between MSA and PBO, difference in remission rates (MADRS < 11) between MSA and PBO, the change from baseline in total score at endpoint of MGH-CPFQ item analysis, difference in change scores on the CGI-S, CGI-I and QIDS. Safety outcome measures: adverse events, physical examinations, vital signs; blood pressure, orthostatic; EKG; Rush Sexual Inventory (RSI).

Statistical Methods: The randomized sample includes all patients who are randomized. The Safety sample will include those randomized patients who received at least one dose of doubleblind study medication as indicated on the dosing record. The efficacy sample will include those patients in the safety sample who have at least one efficacy evaluation post-randomization. The last observation carried forward (LOCF) data set includes data recorded at a given visit after randomization, or, if no observation is recorded at that visit, data carried forward from the previous postrandomization visit. The LOCF data set is primary, and analysis of the observed case data set also will be conducted.

The primary analysis will compare pooled MGH-CPFQ response rates between PBO and MSA and PBO non-responders. Differences in response rates will be compared using the CMH General Association Test. Descriptive statistics on non-primary groups will be conducted.

This study seeks to estimate the strength of any statistically significant relationship, or effect size, in addition to statistical significance of found treatment effects.

Secondary Endpoints Analysis: Differences in remission (defined as an endpoint MADRS score <11) rates will be compared using the CMH General Association Test. Logistic regression analysis will be performed to explore the relationship between response and patients' demographics and prognostic variables including baseline QIDS score, gender, site, and age, etc. Similar analyses will be performed for remission.

Fig. 3	: Stud	y Proce	dures	Table
--------	--------	---------	-------	-------

			Treatment period 1			Treatment period 2			
Study Visit	V1 Screen	V2 Baseline	V3	V4	V5	V6	V7	V8	V9 F/UP
End of Week	-1	0	1	2	3	4	5	6	8
Day	-7	0	7	14	21	28	35	42	56
Informed consent	Х								
Demographic data	Х								

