Medical and psychiatric history	Х	Х							
SCID	х								
Physical exam	Х								
Vital signs and weight	Х	Х	Х	Х	Х	Х	Х	Х	Х
EKG	Х								Х
Lab tests*, urine pregnancy test** and urine drug screen	х								х
MGH-ATRQ	Х								
Inclusion/exclusion criteria	Х	Х							
Randomization		Х							
Expectation ratings		Х							
Clinician-completed surveys:									
HDRS (17- and 28-item)	Х	Х						Х	
MADRS		Х	Х	Х	Х	Х	Х	Х	
CGI-S	х	Х							
CGI-I			Х	Х	Х	Х	Х	Х	
C-SSRS	х	Х	Х	Х	Х	х	Х	Х	х
Patient-completed surveys:									
MGH-CPFQ	Х	Х	Х	Х	Х	Х	Х	Х	
EWPS	х	Х	Х	Х	Х	х	Х	Х	
Fawcett EPI	Х	Х	Х	Х	Х	Х	Х	Х	
FASD	Х	Х	Х	Х	Х	Х	Х	Х	
HSQ 2.0	Х	Х	Х	Х	Х	Х	Х	Х	
PGI-S	х	Х							
PGI-I			Х	Х	Х	Х	Х	Х	
RSI	Х	Х	Х	Х	Х	Х	Х	Х	
QIDS-16	Х	Х	Х	Х	Х	Х	Х	Х	
SANS	Х	Х	Х	Х	Х	Х	Х	Х	
SDS	Х	Х	Х	Х	Х	Х	Х	Х	
SF-36	Х	Х	Х	Х	Х	Х	Х	Х	
Study drug dispensed		Х	Х	Х	Х	Х	Х	Х	
Study drug accountability			Х	Х	Х	Х	Х	Х	Х
Concomitant therapy	Х	Х	Х	Х	Х	Х	Х	Х	Х
Adverse events	Х	Х	Х	Х	Х	Х	Х	Х	Х

*Including CBC and CMP. If patient can produce lab results for CBC and CMP performed within the past 3 months, screening procedures may be waived. **For females of childbearing potential

- Angst J. (1992). How recurrent and predictable is depressive disorder? In: Montgomery S, Rouillon F, eds. *Long-term treatment of depression perspectives in psychiatry*. Chichester, UK: John Wiley & Sons Ltd., Vol. 3, p.13.
- Carvalho AF, Machado JR & Cavalcante JL (2008). Augmentation strategies for treatmentresistant depression. *Current Opinion in Psychiatry*, 22 : 7–12.
- Chiarello RJ & Cole JO (1987). The use of psychostimulants in general psychiatry. *Archives of General Psychiatry*, 44, 286-295.

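### The early-exit visit requires no efficacy scale, so a dosed subject who leaves before any V3 rating drops out of the efficacy sample

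*Combined protocol and SAP*

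**What the plan says.** The section on investigational product and dosing makes intolerance a reason to leave the trial, not only to stop the drug: "Subjects unable to tolerate the study medications will be withdrawn from the study". Study Procedures then states what is done on leaving: "If a subject withdraws or is terminated early from the study, visit 9 procedures will be performed at the final study visit". The same section describes that visit as a safety visit: "Study visit 9: Subjects will return two weeks following visit 8 for a safety follow-up check".

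Fig. 3 agrees. Its V9 column carries vital signs and weight, EKG, laboratory tests, C-SSRS, drug accountability, concomitant therapy and adverse events. Under "Patient-completed surveys", MGH-CPFQ is marked at V1 to V8 and is blank at V9. MADRS, in the clinician block, is marked at V2 to V8. C-SSRS is the only rating scale at V9, and the Statistical Analysis section does not list it as an efficacy endpoint.

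Statistical Methods defines the analysis set: "The efficacy sample will include those patients in the safety sample who have at least one efficacy evaluation post-randomization". On missing data it says: "The LOCF data set is primary, and analysis of the observed case data set also will be conducted". The carry-forward rule uses earlier post-randomization visits only, so baseline is never carried forward.

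The design limits the placebo comparison to Phase 1: "Group 2: PBO during Phase 1 followed by MSA during phase 2".

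**The concern.** Each rule is ordinary taken alone. Together they make membership of the efficacy sample depend on something the drug can affect. A subject who takes study drug, cannot tolerate it and leaves in the first days counts for safety but is absent from efficacy.

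Phase 1 is the only placebo-controlled period, and in it only Group 1 takes MSA. If early intolerance is commoner on MSA, more subjects disappear from Group 1. In a response-rate comparison they leave the denominator when they could have counted as non-responders, and the MSA rate rises although no patient has done better. In a comparison of mean change, the MSA mean is taken over those who tolerated the first week. A rating not taken at exit cannot be recovered later.

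**Working it through.** **Tracing the rules.** Take a subject randomized and dosed after V2 who does not tolerate the drug and leaves before V3.

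| Question | Source | Answer |
|---|---|---|
| In the randomized sample? | Statistical Methods | Yes |
| In the safety sample (at least one dose)? | Statistical Methods | Yes |
| Efficacy scale required at exit? | Study Procedures; Fig. 3, V9 column | No |
| Any post-randomization efficacy rating? | Fig. 3 (first at V3) | None |
| In the efficacy sample? | Statistical Methods | No |
| A value for LOCF to carry? | Statistical Methods | None |

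The mixed model in Study Design does not bring this subject back, because there is no post-baseline score.

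**Where the gap lies.** V3 is at day 7 with a window of 3 days either side, that is days 4 to 10. An exit visit inside those days could be run as V3, with its scales, but the plan does not say that it must be. The clear gap is therefore an exit before day 4, an exit inside the window that is not run as V3, or a subject who never returns.

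**Size.** The plan gives no intolerance rate, response rate, effect size or SD, so there is no figure to reproduce. From the plan: 20 subjects per arm. Everything else below is assumed: k unrated leavers in Group 1, none in Group 2, and x responders among all 20 in Group 1, with unrated leavers counted as non-responders.

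Rise in the MSA response rate = x/(20 - k) - x/20:

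| x | k = 1 | k = 2 | k = 3 |
|---|---|---|---|
| 6 (30%) | +1.6 points | +3.3 | +5.3 |
| 8 (40%) | +2.1 | +4.4 | +7.1 |
| 10 (50%) | +2.6 | +5.6 | +8.8 |

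For x = 8 the rates are 8/19 = 42.1%, 8/18 = 44.4% and 8/17 = 47.1%. For scale, the standard error of a 40% v 20% difference is sqrt(0.4 × 0.6/20 + 0.2 × 0.8/20) = sqrt(0.020) = 0.141, or 14 points.

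Mean change: suppose rated MSA subjects average 0.5 SD better than placebo and unrated ones equal the placebo mean. The overstatement is 0.5 - 0.5 × (20 - k)/20 = 0.5 × k/20, which is 0.025, 0.050 and 0.075 SD for k = 1, 2, 3. The standard error is sqrt(2/20) = 0.32 SD.

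Chance of at least one unrated leaver in Group 1 = 1 - (1 - r)^20. For an assumed r of 2.5%, 5% or 10% per subject this is 40%, 64% or 88%.

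With k = 0 both shifts are zero.

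**The case against.** The strongest reply is that few subjects will be affected. Dosing starts at 5 mg BID, goes up only with clinical judgment and the patient's consent, and can go as low as 5 mg a day, so the dose can be reduced before anyone is withdrawn. An exit on days 4 to 10 can naturally be read as V3 with the visit 9 procedures added. Both points stand. They narrow the gap but do not close it, since nothing in the plan requires the V3 scales at such a visit.

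The sizes are also open to challenge, and rightly. They rest on assumed inputs, including no unrated leavers on placebo. The plan does not define MGH-CPFQ response, and the groups in its CMH comparison need not be 20 v 20. Counting an unrated leaver as a non-responder is itself a choice of estimand. The mean-change example sets unrated subjects at the placebo mean, which is not the same as no change from baseline if placebo subjects improve. The figures show scale and are not estimates.

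A reader might infer that every subject withdrawn for intolerance is lost from efficacy. The documents do not support that. Nothing says the visit 9 procedures replace the scales due at a scheduled visit, and anyone rated at V3 or later stays in through LOCF. For those subjects the direction of any carry-forward error is uncertain.

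A reader might also infer that intolerant subjects must be followed off drug to V5. That answers a different treatment question and goes beyond the one directional bias shown here.

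**Conclusion.** The point holds in a narrow form. Followed exactly, the plan need not obtain any post-randomization efficacy rating from a dosed subject who leaves before V3, and then excludes that subject from the efficacy sample and the primary LOCF data set. The same exclusion applies to a dosed subject who never returns.

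That this would favour MSA is an inference from the design: only Group 1 is exposed to MSA in Phase 1. The documents give no rates by arm, so they do not show that the result would be biased, only that it could be. The size is unknown and probably modest. Under the assumptions above, one to three unrated leavers with 8 MSA responders move the response rate by about 0.15 to 0.5 of a standard error (2.1/14.1 to 7.1/14.1). A shift of that size would not settle the trial's result, but unlike sampling error it would have a direction, and it is cheap to avoid.

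**What to change.** 1. In Study Procedures and Fig. 3, require MGH-CPFQ and MADRS at the early-termination visit, in addition to the visit 9 procedures and any scales already due at that visit.
2. In Statistical Methods, report by arm every dosed subject without a post-randomization rating, including those who never return, whom step 1 cannot reach. Add a sensitivity analysis that keeps these subjects in their randomized arm as no change from baseline, and as non-responders in any CMH analysis.

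The cost is a short amendment, two existing scales at one visit, and one extra analysis. There are three downsides. The exit rating is still an early score. It may reflect recent discontinuation, a risk the plan recognises when at V8 it gives "instructions for tapering the dose of the MSA to avoid potential difficulties from abrupt discontinuation of the study drug". The estimated effect may also be smaller. Withdrawal decisions stay with the investigator.

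Off-drug ratings through V5 for willing subjects are an option the sponsor could consider, not a required correction.

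### Discontinued subjects have no scheduled all-cause collection of serious adverse events after their final visit, while completers have 14 days after Visit 8

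*Combined protocol and SAP*

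**What the plan says.** Under Monitoring and Reporting of Adverse Events and Serious Adverse Events, the general rule ignores causality: "All observed or volunteered adverse events, regardless of suspected causal relationship to study drug, will be recorded on the case report form". The rule for events after discontinuation is different: "Serious adverse events occurring after a subject is discontinued from the study will not be reported unless the investigator feels". The exception that follows is worded as possible causation: "that the event may have been caused by the study drug or a protocol procedure". No criteria and no time limit go with that judgement.

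The Risk/Safety Information section requires follow-up of events that are serious or that led to discontinuation: "The subject should be followed until the event resolves or is explained".

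On timing, Study Procedures says of completers: "Subjects will return two weeks following visit 8 for a safety follow-up check". Of the others it says: "If a subject withdraws or is terminated early from the study, visit 9 procedures will be performed at the final study visit". In Fig. 3 the last marked adverse event collection is Visit 9, day 56.

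Two further statements concern the time after Visit 8. At that visit "study subjects will be provided a one-month prescription for the dose of MSA they are currently prescribed in the study". After the study, "subjects will be followed for up to three months while an appointment can be secured"; no adverse event collection is attached to this follow-up. Study Procedures and the dosing section also say that MSA is tapered from Visit 8.

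**The concern.** Completers and discontinuers are observed for serious harm under different rules. For a completer, any SAE in the two weeks after Visit 8 falls within scheduled collection. For a subject who leaves early, scheduled collection ends at the final visit. A later SAE is reported only if the investigator thinks drug or procedure may have contributed.

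Both kinds of subject stay in the Safety sample, which requires only one dose of blinded drug. A discontinuer therefore counts in the denominator while a later SAE may be missing from the numerator. The protocol withdraws subjects who cannot tolerate study medication, so the rule applies to people in whom later harm is of particular interest. In major depression, a hospitalisation or suicide attempt soon after leaving can readily be put down to the illness.

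Hypothesis 2a claims acceptable safety and tolerability compared with placebo. That contrast is concurrent only in Phase 1, because both groups are assigned MSA in Phase 2. SAEs missed after Phase 1 discontinuation are therefore the ones that can distort it.

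**Working it through.** **Inputs.** Fig. 3: Visit 1 at day -7, Visit 5 (end of Phase 1) at day 21, Visit 8 at day 42, Visit 9 at day 56. Study Design: visit window of 3 days either way. Number of Subjects: 40 randomised, 20 per arm, with replacement only to secure 24 evaluable.

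**1. The plan's own figures.** Length of participation = (56 - (-7)) / 7 = 63 / 7 = 9 weeks, as stated. Visit 8 to Visit 9 = 56 - 42 = 14 days, the stated two weeks. The schedule is internally consistent.

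**2. Scheduled all-cause collection after the last treatment-period visit.**

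| Subject | Scheduled collection | Rule for a later SAE |
|---|---|---|
| Completer | 56 - 42 = 14 days after Visit 8 | None stated after Visit 9 |
| Discontinuer | 0 days after the final visit, where Visit 9 procedures are done | Reported only if the investigator feels drug or procedure may have contributed |

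If the 3-day window applies to both visits, the 14 days range from (56 - 3) - (42 + 3) = 8 to (56 + 3) - (42 - 3) = 20. The zero for discontinuers counts from the final visit. The time from last dose to that visit is not stated, so this is not a claim of zero days after the last dose.

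**3. How many subjects could be affected.** The plan tolerates 40 - 24 = 16 non-evaluable subjects (16 / 40 = 40%) before replacement is needed. This is an allowance, not a forecast: no discontinuation rate is given, and not every non-evaluable subject need be a discontinuer.

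**4. Scale of one event.** One SAE in an arm of 20 is 1 / 20 = 5 percentage points. This holds for any event in an arm of that size. It shows how coarse the comparison is and does not estimate how many events would be missed.

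**5. Completers with the one-month prescription, taken as written.** End of supply = 42 + length of month; uncovered days = end of supply - 56.

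| Month | Supply ends | Uncovered days | Share of supply |
|---|---|---|---|
| 28 days | day 70 | 14 | 14/28 = 50% |
| 30 days | day 72 | 16 | 16/30 = 53% |
| 31 days | day 73 | 17 | 17/31 = 55% |

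With opposite 3-day shifts of Visits 8 and 9 the gap runs from 14 - 6 = 8 to 17 + 6 = 23 days. All these figures depend on the prescription being used as written. The taper has no stated length; if it ended by day 56, the gap would be zero.

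**The case against.** There are good arguments on the other side, and several limit the point.

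- **The exception is wide.** A reader who stops at the first half of the sentence might infer that only drug-caused events are reported. The test is possible causation, and it includes procedures. That bar is low, but it still decides whether an event is reported at all, and no criteria are given.
- **The sentence may concern IRB reporting only.** It closes a paragraph on what the site sends to the IRB, and the case report form rule carries no cut-off at discontinuation. It would go too far to say that SAEs are certain to go uncounted. But that rule covers events observed or volunteered, and nothing schedules observation of a discontinuer after the final visit.
- **Known events are followed.** Serious events and those causing discontinuation are followed to resolution, which keeps the site in touch with some discontinuers. This does not provide for finding new events.
- **The direction of bias is not established.** A reader might infer that the rule favours MSA because intolerance would be commoner on it. The documents give no discontinuation rates by arm, and a filter that drops events attributed to the illness could equally remove worsening on placebo.
- **The prescription gap is conditional.** A reader might infer that about half of the supplied MSA is certainly taken unobserved. The taper from Visit 8 contradicts that reading, and the prescription, given after unblinding to ease transfer of care, can be read as post-trial care.
- **Events after Visit 8 do not bear on the placebo contrast,** since both groups are assigned MSA in Phase 2.

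**Conclusion.** The point holds as one of uneven ascertainment. Completers have 14 days of scheduled all-cause adverse event collection after Visit 8. Discontinuers have none after their final visit, and their later SAEs pass through a judgement without criteria, although both groups belong to the Safety sample. For subjects who leave in Phase 1 this can distort the MSA-versus-placebo comparison in hypothesis 2a. Neither direction nor amount can be computed, because the documents give no SAE or discontinuation rates.

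The gap of 14 to 17 days between the end of the prescribed supply and the last scheduled collection is a separate, conditional matter. It assumes that the prescription stands as written and that a month is 28 to 31 days. It bears on the overall count of harms on MSA. The documents do not support the stronger readings that the rule is biased in favour of MSA or that serious events are certain to be lost.

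**What to change.** Keep adverse event collection from Visit 1 as in Fig. 3, and replace the sentence on events after discontinuation with wording such as:

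*All SAEs, whatever their suspected cause, are recorded on the case report form and reported until at least 14 days after the last study dose, and no earlier than Visit 9 for completers. This applies to every treated subject, completed or discontinued. Causality is assessed after reporting. Beyond this window, SAEs are reported if the investigator considers that study drug or a protocol procedure may have contributed.*

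The 14 days match what the plan already schedules for completers after Visit 8. The cost is one brief safety contact per discontinuer, for example by telephone, and a few more unrelated events to report.

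Separately, reconcile the taper from Visit 8 with the one-month prescription at the current study dose, and state whether drug taken after Visit 8 counts as study drug, since this determines the last study dose. If the prescription stands as written, attach an SAE question to any contact made during the follow-up of up to three months. That follow-up has no scheduled contacts and no minimum length, so on its own it does not guarantee coverage to day 70 to 73.
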